2.0 Introduction

Post-traumatic stress disorder (PTSD) occurs in as many as 1 in 5 combat Veterans¹⁵⁻¹⁷ and is associated with a host of negative, long-term consequences, including high rates of suicide and traumatic death.^{47,48} Trauma-focused cognitive-behavioral therapies for PTSD, like Prolonged Exposure Therapy (PE), result in significant improvement for many patients.²² While these proven psychotherapies have been disseminated in VA, poor adherence interferes with treatment response.^{49,50} Previous reviews of treatment completion in randomized controlled trials find that one in five patients dropout from active, change-focused treatments for PTSD, including PE and Cognitive Processing Therapy (CPT).²⁶ Rates of PE/CPT drop out are even higher

among Veterans,^{27-29;50;51} with estimates across studies converging around 35%.²⁷⁻²⁹ Importantly, those with the greatest need for PTSD treatment are likely at the highest risk for premature termination.²³ Similar problems with tolerating treatment are found among cognitive behavioral therapies, broadly.²⁶ Consequently, adherence, in and of itself, was identified as a top priority for real-world use of Evidence-Based Practices (EBPs) by the World Health Organization, Institute of Medicine, and the US Surgeon General.^{22;32-34}

PE addresses PTSD through confronting trauma memories to reduce fear, facilitate emotional processing, and promote new learning.⁵² Disrupting entrenched patterns of avoiding trauma reminders requires persistence by Veterans, through daily trauma exposure exercises at home. While these exercises require considerable Veteran commitment, they are similar to those of other demonstrated, effective, cognitive-behavioral therapies,⁵³ and psychotherapies with homework are associated with better treatment outcomes.^{25;54} Meta-analysis indicates 24% more patients will improve just from adding homework to a given psychotherapy.⁵⁴ Across multiple meta-analyses, compliance with these assignments predicts treatment response.^{24;25;53;56;57} Additionally, adherence to more challenging homework assignments, like exposure

[figure not shown]

Figure 1. Conceptual Model Underlying Partner Supported PE

exercises, predicts treatment response better than adherence to less difficult exercises (i.e., readings, self-monitoring).⁵⁵ Ultimately, the key for optimizing Veterans' gains from PE likely lies with efforts to maximize Veterans' engagement, through

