5.5A.3 Exploratory Aim. Exploratory Aim outcomes (key social influences) will be measured from self-reports from both Veterans and SPs at Baseline, Posttreatment, and Weekly intervals. The frequency of measurement is necessary for examining the nature, shape, and change of key social influences week-by-week over the course of treatment. For the IC phase, the Weekly self-report for Veterans will be completed before each treatment session with a \$5 incentive for each form. IC phase participants will only receive these assessments for the first 3 weeks of treatment (session 2a and 2b). For the RCT phase, Veterans and SPs will be given surveys during weeks 2, 4, 5, 6, 8, 10 and 12 of treatment. Participants will be compensated \$10 for completing each survey during weeks 4, 5, 6, 10 and 12. The weekly surveys during week 2 and 8 will be lengthier and more thorough, thus participants will be paid \$20 for completing weekly surveys on those two weeks of treatment. Staff will make reminder calls to Veterans to ensure these weekly surveys are completed and offer telephone administration. SP data collection will take place by mail or online, because if SPs in standard PE receive assessments with Veterans at the medical center, we may unintentionally increase the rates of SPs reaching out to providers, artificially inflating family assistance within standard PE (i.e., cross-over effects). Veteran and SP participants are required to complete their baseline assessment survey before beginning treatment, as the baseline survey is part of study eligibility criteria. Participants will be given a \$40 incentive for the baseline surveys. Veteran and SP participant posttreatment assessments will be administered using CCDOR's modified-Dillman protocol, with a \$50 incentive for Posttest surveys, as well as a post-card reminder, second and third survey mailing package, telephone call reminders, and an offer of telephone administration to optimize response rates.⁶ For Weekly assessments, SPs from both conditions will receive a packet of self-report forms and postage paid envelopes at study enrollment (RCT only, these measures will be administered in person when SPs attend sessions in the IC phase). SPs will mail completed self-report forms to staff weekly and receive their incentive for each completed form. Study staff will make reminder calls each week to participants to complete the weekly survey. If study staff fail to reach a participant, another weekly survey will be sent along with a letter reminding him/her to complete the survey and mail back to the VA. For the few sessions that SPs in family supported PE attend, they will be offered in person administration of their weekly forms for convenience. We will also send Veterans and SPs a follow-up survey 3 months after the posttreatment assessment. Participants will receive a \$60 incentive for completing the 3 month follow-up survey, and we will use CCDOR's modified-Dillman protocol once again to optimize response rates. See attached Materials for study measures.

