5.5A.6 Covariates. SP support for PE may better influence adherence with less SP distress, less family conflict, greater provider-SP contact, and certain demographic characteristics (e.g., gender, age, or race/ethnicity). SP distress will be assessed using the PROMIS Perceived Stress scale⁹⁸ and General Functioning scale of Family Assessment Device (FAD). Frequency of provider-SP contact will be assessed in weekly provider reports. Demographic variables such as race, gender, SP-Veteran relationship (e.g., spouse, parent, adult child), and frequency of SP-Veteran contact will also be assessed at Baseline.

5.5A.7 Qualtrics Online Surveys

Survey administration format will transition to Qualtrics FedRAMP electronic survey software accessed via the VA cloud. This transition will support data collection during the current COVID 19 directives. Our study sites have been ordered to "shelter in place" during the pandemic, making paper survey mailings unachievable. Paper surveys will still be available to those who need or request them, but we plan to use online surveys as our primary modality.

Qualtrics FedRAMP has been approved for use from the VA OIT Security standpoint (Authority to Operate or ATO). The ATO status is currently approved for 1 year and a full 3-year ATO is in the works. Qualtrics FedRAMP surveys will contain a study ID number, time of data entry and limited individually identifiable information. Within the VA firewall, the study team at the VA will create a custom- built tracking app that will track each participant's enrollment and study status. Data will be routinely extracted from Qualtrics FedRAMP in the VA cloud and stored on secure CCDOR servers, using SQL database connections. All data will be stored and utilized within secure CCDOR servers that are part of the Minneapolis VAMC network and which operate behind the VA firewall. All data is tracked using a SQL database, with a GUI-front end system that restricts access to only those with approval to study data.

Qualtrics FedRAMP surveys will contain minimal individually identifying information. The only identifying information will be information that is self-reported by the participants (e.g. name, phone, email, which is best method of contact). No sensitive data will be stored outside of the VA protected environment. Once data are transferred for data analysis, data will be maintained on password-protected VA computers in the VA environment and on secure VA servers.

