Power analyses are based upon our ability to detect a clinically meaningful difference between our two treatment conditions on PTSD symptom severity using the PCL.⁵ A five-point difference on the PCL is the minimal threshold for determining if an individual has responded to treatment (i.e., differences not due to chance); a ten point difference is the minimal threshold for clinically relevant differences.⁷ Smaller differences are unlikely be clinically meaningful. Analyses take into account our repeated measures, two-armed design and estimates of variance and auto-correlations between repeated PCL assessments from our prior work (Project HomeFront, Time 1 PCL SD = 12.16; Time 2 PCL SD = 14.8; Time 1 and Time 2 PCL, $r = .61$). Using a plausible range of auto-correlations ($r = .50\text{-.70}$) and standard deviation estimates (SD = 12.16-14.8), and assuming 20% missingness on posttreatment PCL scores ($n = 124$), we are sufficiently powered (80%) to detect a 4.1 to 5.8 point difference between treatment conditions on posttreatment PCL total scores ($d = .34\text{-.40}$). Analyses will rely on the latest version of the PCL (i.e., the PCL-5²). Data currently is unavailable translating clinically meaningful differences on the PCL to the PCL-5; however, preliminary work suggests the ranges described above will be similar for the PCL-5.²

5.6B. Data Analysis.

5.6B1. General Approach. The study is a two arm patient-level randomized superiority trial, nested within 3 sites, each with 4 providers. Analyses will consider this design structure and follow intent-to-treat methodology. First, we will examine the distribution of all study variables (data verification). Second, we will evaluate bivariate associations between condition assignment and study outcomes and covariates to determine unadjusted measures of effect and identify imbalance in baseline covariates. Due to randomization, we do not anticipate imbalances in baseline characteristics between groups, but we will adjust for any differences by including these variables as covariates. Third, we will examine the impact of missing survey items and adjust for their influence. After testing and identifying the mechanism underlying any missingness (MAR,NI), we will use the implied specific imputation methods to impute missing covariates and factors and generate five imputed data sets. Final analyses will include complete case analysis and an aggregated analysis based on the multiply imputed data.

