5.6B2. Aims 1 and 2. After completing the above steps, we will test our hypothesis for Aim 1 using generalized linear mixed models. The number of sessions attended, within the assumed and appropriate fitted distribution, will be modeled with treatment and site as fixed effects and a random provider effect (clustering by provider). Analyses for Aim 2 will similarly use mixed models to examine differences between conditions on PCL-5 scores over time, modeling the treatment, time, and treatment by time effects. Secondary analyses will examine CAPS-5 scores and loss of diagnosis on the CAPS-5 (both PTSD diagnosis and subclinical PTSD diagnosis) to facilitate comparisons with existing and ongoing research on treatments for PTSD. We will also examine differences between conditions on PHQ-9, WHO-QOL, QRI, and CSQ-8 scores.

Analyses will follow the same general approach as Aim 1, with some exceptions. First, some indices are dichotomous (i.e., presence or absence of PTSD or subclinical PTSD diagnosis). Models will be fit using appropriate distribution and link functions (i.e. for binomial distribution and logit links for PTSD diagnosis; whereas mean group differences might fit a normal distribution). Second, unlike Aim 1, which relies on administrative data, Aim 2 outcomes rely on

self-report data, where some attrition is inevitable. Analyses will include examining group differences using available data, as well as analyses employing imputation as described above. To study the time-dependence of clinical outcomes, we will model the first-order transition probabilities of Markov chains (under treatment and control) with auto regressive random intercepts, random slope (provider), and fixed effects for treatment, site, sessions attended, and homework compliance. Lastly, we will explore indirect pathways from family supported PE to improved treatment outcomes through greater adherence (e.g., treatment condition → session attendance → PTSD symptoms), using approaches for testing indirect effects described below.

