5.6B4. Exploratory Aim. For this Aim, we will test if differences between family supported PE and standard PE are mediated by the key social influences targeted by family supported PE (e.g., treatment condition → family support for PE participation → session attendance). Mediators include weekly scores on the CEQ-PTSD⁹⁶ (SP report), SORTS⁹⁷ (SP report), and Support Checklist (Veteran report). Analytic approaches will be similar to Aim 1, with social influence variables incorporated as mediators. This basic mediation model is a special case of random effects structural modelling, where each equation will have random intercept and provider terms, adjusted for site fixed effects. Indirect effects for mediators treated as single summary scores will be directly tested using bootstrapped confidence intervals¹⁰⁵ to avoid the often-violated assumption underlying Sobel's (1982) method that the sampling distribution of the indirect effect is normal. Analyses will also examine differences between conditions on the rate and shape of change in key social influences.

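### The exploratory mediation equations do not prespecify the baseline mediator or baseline PCL-5, so the non-randomised mediator-to-outcome path is open to confounding that two covariates already collected would reduce

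*Combined protocol and SAP*

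**What the plan says.** Section 5.6B4 tests whether arm differences in adherence run through social-influence scores: CEQ-PTSD and SORTS from the support person, and the Support Checklist from the Veteran. It states: "Analytic approaches will be similar to Aim 1, with social influence variables incorporated as mediators". It adds that "each equation will have random intercept and provider terms, adjusted for site fixed effects". The Aim 1 model in 5.6B2 has treatment and site as fixed effects and provider as a random effect. Indirect effects for single-summary mediators are tested with bootstrapped confidence intervals.

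Section 5.6B2 also plans to "explore indirect pathways from family supported PE to improved treatment outcomes through greater adherence", using the same indirect-effect methods.

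Other sections mention covariates:

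- 5.6B1, on baseline differences between arms: "but we will adjust for any differences by including these variables as covariates".
- 5.5A.6: "SP support for PE may better influence adherence with less SP distress, less family conflict, greater provider-SP contact, and certain demographic characteristics". It then lists measures of support-person distress and family functioning, provider contact and demographics.
- 5.3: support-person attendance.
- 5.1G: provider fidelity and competence.

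None of these names a baseline mediator score or baseline PCL-5. Both kinds of score are in the data plan. Section 5.5A.3 says the social influences "will be measured from self-reports from both Veterans and SPs at Baseline, Posttreatment, and Weekly intervals", and 5.5A.4 has PCL-5 at baseline.

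**The concern.** Condition is randomised; attendance and family support are not. A Veteran who starts with more support, or with milder PTSD, may later show both a better mediator value and a better outcome for reasons that have nothing to do with the mediator. If the intervention also moves the mediator, the product of the two paths is then non-zero with no causal mediation behind it.

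The protocol itself gives reason to expect such a common cause. Section 2.0 says that "those with the greatest need for PTSD treatment are likely at the highest risk for premature termination", and 5.6A2 reports a correlation of .61 between PCL scores at two times. Severity could therefore lower attendance and raise later symptoms.

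What is at stake is the mechanism account: that family involvement works through social influence, and that better adherence carries the benefit to symptoms. The comparisons between arms on attendance and on PCL-5 are not touched.

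**Working it through.** **Inputs from the documents.** 78 per arm, 156 in total; SD of sessions attended 4.45; target difference 2 sessions (5.6A1). PCL SD 12.16 at Time 1 and 14.8 at Time 2, r = .61 (5.6A2; these come from Project HomeFront and the earlier PCL, not the PCL-5). 12 providers with 13 patients each (5.1A).

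**Assumed.** The correlation ρ between baseline severity and attendance, for which the documents give no value: -.1, -.2, -.3. Two-sided 5% level (not stated). True mediator effect zero.

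**The plan's own figure.** n per arm = 2 × (1.96 + 0.842)² × 4.45² / 2² = 77.7, so 78, as stated. The standardised arm difference used below is 2/4.45 = 0.449. No power or effect size is given for mediation.

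**Size of the spurious effect, attendance to PCL-5.** With attendance having no effect on symptoms, the attendance slope without baseline PCL is:

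- Posttreatment score as outcome: b = ρ × .61 × 14.8 / 4.45 = 2.029ρ PCL points per session. Indirect effect = 2 × b = 4.06ρ.
- Pre-to-post change as outcome: b = ρ × (.61 × 14.8 - 12.16) / 4.45 = ρ × (9.028 - 12.16) / 4.45 = -0.704ρ. Indirect effect = -1.41ρ.
- Baseline PCL as a covariate in both equations: expected b = 0. The posttreatment and change forms then give the same attendance slope.

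**How often it is declared** (simulation, n = 156, 95% interval for the product of paths):

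| ρ | Posttreatment: spurious effect | False benefit | Change: spurious effect | False harm | Baseline PCL included, either direction |
|---|---|---|---|---|---|
| -.1 | -0.41 | about 8% | +0.14 | about 3% | about 3-4% |
| -.2 | -0.81 | about 24% | +0.28 | about 6% | about 3-4% |
| -.3 | -1.22 | about 49% | +0.42 | about 12% | about 3-4% |

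Negative values mean fewer symptoms. A percentile-bootstrap version with provider terms gave 12%, 24% and 45% for the posttreatment column, so the pattern does not depend on the interval method. The 3% in the first change-score row is close to the 2.5% expected in one tail, so at ρ = -.1 that form shows almost no excess.

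**Does the arm-imbalance rule help?** It acts on differences between arms, whereas this confounding lies within arms. It was checked for a social-influence mediator on an assumed grid (provider terms, 1,500 trials per cell, rule read as p < 0.05). In the cell with a mediator shift of 0.45 SD, baseline-to-mediator correlation 0.5 and baseline-to-outcome link 0.3, false mediation was 34.5% as stated, 33.7% with the rule, and 4.0% with baseline support and severity in both equations. Over all confounded cells in which treatment moves the mediator, the range was 9% to 86% unadjusted and 3.5% to 5.6% adjusted. Where treatment does not move the mediator, the rate was at most 3.3%.

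**Limits.** Normal outcomes stand in for a session count, the mediator is a single summary score, and PCL data are complete. The 20% missingness allowed for in 5.6A2 would lower the rates somewhat. It would leave the spurious effect where it is, if missingness is unrelated to these variables.

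**The case against.** A reader might infer that the mediation equations contain only treatment, mediator, site and provider. The documents do not support that. Section 5.6B4 describes a model structure rather than a closed covariate list, and 5.5A.6, 5.3, 5.1G and 5.6B1 bring in other variables. What stands is narrower: no text names baseline support or baseline PCL-5. Support-person attendance and fidelity arise after randomisation, so they cannot stand in for a baseline score.

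A reader might also infer that the trial is heading for a false claim that adherence lowers symptoms. That depends on the form of the outcome. Section 3.0 states Aim 2 as pre-to-posttreatment improvement, and 5.6B2 models PCL-5 over time, so baseline may already enter. Under a change score the bias shrinks and turns towards apparent harm. This objection is right about direction and size. It does not remove the problem, because 5.6B2 does not say which form the indirect path uses and some bias remains under both. Likewise, section 3.0 speaks of changes in social influences, and the social-influence grid above used a level, so its rates do not describe a change mediator.

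The severity link is also softer than it may seem. Section 2.0 speaks of need and of likelihood; it does not report that baseline PCL-5 predicts sessions attended.

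Finally, the adjusted rates look clean because the simulations contain no other confounder. Baseline covariates cannot remove confounding that develops during treatment. And the work is labelled exploratory, which limits the consequences but is no reason to leave out covariates already in hand.

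**Conclusion.** The point holds as a gap in prespecification. Sections 5.6B4 and 5.6B2 leave the baseline mediator and baseline PCL-5 out of the stated mediation equations, no other section supplies them, and the arm-imbalance rule does not address the resulting bias.

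False mediation beyond the nominal level needs two conditions: the intervention moves the mediator, which is its purpose, and baseline severity or support affects the mediator and also the outcome by another route, which section 2.0 makes plausible for severity. For attendance to PCL-5, the size runs from little or no excess (weak correlation, change score) to about half of trials (ρ = -.3, posttreatment score). The correlations are assumptions, so these figures show what can happen, not what will.

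This is a free improvement to the exploratory analyses. It is not a defect in the primary comparison.

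**What to change.** In 5.6B4, state that both the mediator equation and the outcome equation include the baseline value of that mediator, where it is taken at baseline, and baseline PCL-5. The qualifier matters for the Support Checklist: its items concern past-week behaviour around PE attendance (5.5A.5), which may have little meaning before PE starts.

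In 5.6B2, state that both equations of the condition-attendance-PTSD path include baseline PCL-5. This is needed whether the outcome is the posttreatment score or the change.

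Add one sentence saying that confounding arising after baseline remains, so the indirect effects are exploratory.

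The cost is wording only. Section 5.3 requires both members of the dyad to complete the baseline survey before randomisation, so no new data, visits or participants are needed.

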5.7 Withdrawal of Subjects

Participants can withdraw from the study at any point in time and for any reason by contacting study personnel in person, by telephone, or by mail, and requesting to withdraw. We anticipate termination of participation if:

1. The participant becomes ineligible to participate
2. The participant does not follow instructions from the researchers

3. The study is unexpectedly suspended or canceled.

6.0 Reporting

We will follow the VA Central IRB Table of Reporting Requirements for all issues that must be reported (i.e. summary of adverse events, unexpected problems and any actions or changes with respect to the protocol).

Adverse events (AE) include any untoward medical occurrence in a patient or clinical investigation subject administered an intervention and which does not necessarily have a causal relationship with this treatment. We will collect the following safety information (adverse events) that occurred within 7 days leading up to the final assessment.

1. Suicide attempts
2. Hospitalizations for mental health
3. Episodes of family violence

Therapists will be instructed to notify study staff immediately when such events occur during treatment delivery. Staff will report directly to the local site PI regarding any events. Counselors will also meet regularly by phone for case consultation with a study investigator, where the occurrence of any of these events will be further discussed and tracked. Questions regarding the occurrence of each of these three events will be included in posttreatment assessments. Data obtained from participants will be reviewed for safety concerns. In the case of problems, the staff will discuss this with the appropriate site PI.

Of note, survey reports of IPV on posttreatment and follow-up surveys will be reported when respondents endorse items consistent with severe violence. This includes the following: (1) hit my partner with a fist or something hard, (2) kicked my partner, (3) slammed my partner against something, (4) beat my partner, (5) burned my partner on purpose, (6) tried to hurt my partner by choking or suffocating him/her, or (7) used a knife or gun on my partner. Examples of serious adverse effects, according to the FDA, include death, life-threatening adverse events, suicide attempts, and hospitalization. Consequently, endorsement of items 6 or 7 will be considered a SAE. Given the population, some incidents of severe IPV are expected. Reports of severe IPV on baseline surveys are part of our exclusionary criteria (see inclusions/exclusions). Thus, severe IPV in reported in baseline surveys will not be reported as adverse events.

All site PIs are licensed clinical psychologists. Events will also be immediately communicated to the study PI, who is also a licensed clinical psychologist. The PI in turn will report any problems to the central IRB. Once learned of any SAEs, UAP, compliance issues, RCO, and/or protocol deviation from the study coordinator or local site PIs, the study PI will report these events as defined by the VA Central IRB Table of Reporting Requirements to the VA Central IRB. The study PI will complete the appropriate forms (i.e. 119 or 129) as listed on the VA Central IRB Table within 5 business day of learning of its occurrence. If there are modifications or amendments to the study the study PI will also complete the appropriate Central IRB form (i.e. 116) and wait for approval prior to implementation.

